5.2.2 If subjects withdraw before/during Month 12 due to		
5.2.2.1 Safety reasons (e.g. AE/death, liver chemistry stopping criteria, renal toxicity withdrawal criteria, QTc withdrawal criteria etc, as recorded in eCRF Conclusion form)	No virologic data at Month 12 Window	Disc due to AE/death
5.2.2.2 Non-safety related reasons (e.g. Lack of efficacy, protocol deviation, withdrew consent, loss to follow-up, study closed/terminated, investigator discretion et al, as recorded in eCRF Conclusion Form)		
Last on-treatment VL <50 c/mL OR no on- treatment VL available during study	No virologic Data at Month 12 Window	Disc for other reasons
Last on-treatment VL ≥ 50 c/mL AND withdrawal due to Lack of efficacy	HIV1-RNA ≥ 50	Disc. for lack of efficacy
Last on-treatment VL ≥ 50 c/mL AND withdrawal due to all other non-safety related reasons	HIV1-RNA ≥ 50	Disc. for other reason while not below 50

a: Excluding permitted change in background therapy where change or decision to change is made prior to/on the first on-treatment viral result

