#### 2. SUMMARY OF KEY PROTOCOL INFORMATION

## 2.1. Changes to the Protocol Defined Statistical Analysis Plan

The following are changes or deviations to the originally planned statistical analysis specified in the 209035 protocol amendment 1 [(Dated: 22/JUN/2018)]:

[figure not shown]
- PK samples would not be analysed and no PK outputs would be produced. Due to the
  vast amount of PK data available from other studies examining CAB LA + RPV LA
  PK data, CPMS decided not to evaluate PK data from this study. Additionally, the
  time points of PK sample collection correspond to peak, rather than trough,
  concentrations.
- Data from the digital assistance program was not collected due to cost concerns of using Ensemble and will not be analysed.

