#### 7.1.1. Endpoint / Variables

Proportion of participants with plasma HIV-1 RNA  $\geq$  50 copies/mL as per Food and Drug Administration (FDA) Snapshot algorithm at Month 12.

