#### 7.1.2. Summary Measure

Number of subjects and percentage of participants with HIV-1 RNA ≥50 c/mL at Month 12 (defined by the US FDA snapshot algorithm) will be provided by treatment group.

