## 12.9. Appendix 9: Snapshot Algorithm Details

### **Detailed Algorithm Steps**

- Consider an analysis visit window for Month X as defined in Table 8 and Table 9.
- The HIV1-RNA threshold of 50, copies/mL will be analysed, in this study
- The analysis window 'Month 12' and HIV1-RNA threshold of '50 copies/mL' are used for the purpose of illustration. A subject's Snapshot response and reason at Month 12 are categorized as below.
  - HIV1-RNA < **50** copies/mL
  - o HIV1-RNA ≥ **50** copies/mL

Data in window not below 50
Discontinued for lack of efficacy
Discontinued for other reason while not below 50
Change in background therapy\*

Discontinued study for other reasons
On study but missing data in window

 The steps in determining response and reasons are indicated in Table below, in the order stated.

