#### **Examples from FDA guidance**

#### Data in Window

Virologic outcome should be determined by the last available measurement while the patient is on treatment and continued on trial within the time window:

• HIV-RNA = 580 copies/mL at Day 336, HIV-RNA below 50 copies/mL on Day 350. This should be categorized as HIV-RNA below 50 copies/mL.

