#### Discontinued for Other Reasons:

- Only patients who have achieved virologic suppression can be counted as *Discontinued* for Other Reasons.
- If a patient discontinues the study before the time window because of *lack of efficacy* then the patient should be included in the HIV-RNA greater than or equal to 50 row and not in the Discontinued for Other Reasons row.
- If a patient discontinues because of subject withdrew consent and his or her HIV-1 RNA
  result at the time of discontinuation was equal to or above 50 copies/mL, then he or she
  should be categorized as HIV-RNA greater than or equal to 50 and NOT as
  Discontinued for Other Reasons.
- If a patient discontinued because of *Lost to Follow-Up* and the last HIV-RNA result was 49 copies/mL, then the patient can be categorized as Discontinued for Other Reasons.
- If patients changed background treatment *not permitted by protocol* they should be captured in the HIV-RNA greater than or equal to 50 copies/mL row.

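### Snapshot step 5.2.2.2 puts a pre-window lack-of-efficacy withdrawal with last on-treatment viral load <50 c/mL, or none, under no virologic data; the FDA rule reproduced in the same appendix counts it as HIV-1 RNA ≥50 c/mL

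*SAP*

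**What the plan says.** SAP 7.1.1 defines the primary endpoint as the proportion with HIV-1 RNA ≥50 c/mL "as per Food and Drug Administration (FDA) Snapshot algorithm at Month 12". Appendix 9 (SAP 12.9) makes the step table operative: "The steps in determining response and reasons are indicated in Table below", and the steps are applied in sequence. Steps 1 to 4 deal with changes in antiretroviral therapy, step 5.1 with participants who have a viral load in the window, and step 5.2 with those who have none.

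Step 5.2.2.2 covers withdrawal before or during Month 12 for non-safety reasons and names lack of efficacy as one of them. Its first row, "Last on-treatment VL <50 c/mL OR no on- treatment VL available during study", leads to no virologic data with the reason recorded as discontinued for other reasons. Its second row gives ≥50 c/mL for lack of efficacy, but only if the last on-treatment value is also ≥50 c/mL. Its third row gives ≥50 c/mL for the remaining non-safety reasons on the same viral-load condition.

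The appendix then reproduces "Examples from FDA guidance". Under discontinuation for other reasons, the first bullet begins "Only patients who have achieved virologic suppression can be counted as" discontinued for other reasons. The second bullet takes discontinuation before the window because of lack of efficacy and says "then the patient should be included in the HIV-RNA greater than or equal to 50 row", and not in the other-reasons row. It attaches no viral-load condition.

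SAP 2.1, introduced by "The following are changes or deviations to the originally planned statistical analysis specified in the 209035 protocol amendment 1", lists two items: the PK samples and the digital assistance programme. The Snapshot rule is not among them.

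**The concern.** Within step 5.2.2.2 the reason lack of efficacy never changes the response. It changes only the label once the viral load is already ≥50 c/mL. In the reproduced FDA rule the reason alone decides the response. A programmer working from the table and a reader working from the examples would therefore classify the same participant differently on the primary endpoint.

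The difference has one direction. Programmed as written, the table can only reduce the number counted as ≥50 c/mL relative to the algorithm the SAP names. The same classification feeds the ITT-E and per-protocol outcome tables, the by-visit and subgroup tables, and the by-visit figure with 95% confidence intervals (SAP 12.12.5 and 12.12.6).

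**Working it through.** **1. Where the two rules differ.** Consider withdrawal before the window, no viral load in the window, and no earlier classification by steps 1 to 4. Cross three reasons with four values of the last on-treatment viral load (none, 49, 50, 300 c/mL).

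| Reason | Last on-treatment value | Step 5.2.2 | FDA examples in Appendix 9 |
|---|---|---|---|
| Adverse event | any of the four | no data | no data |
| Lack of efficacy | none | no data | **≥50** |
| Lack of efficacy | 49 | no data | **≥50** |
| Lack of efficacy | 50 or 300 | ≥50 | ≥50 |
| Other non-safety | none or 49 | no data | no data |
| Other non-safety | 50 or 300 | ≥50 | ≥50 |

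The rules disagree in 2 of 12 combinations, both for lack of efficacy. The other-reason row with no value is read as suppressed, since entry required <50 c/mL.

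**2. When step 5.2.2 is reached in the Q2M arm.** The Month 12 Snapshot window is Days 285 to 375 (SAP Table 8). On-treatment time ends 67 days after the last injection if there is no later oral CAB + RPV (SAP Table 15). With injections on target days:
- last injection at Month 8: 211 + 67 = Day 278, before the window opens, so no on-treatment value can fall in it;
- last injection at Month 10: 271 + 67 = Day 338, so a value in the window is possible and step 5.1 would then apply.

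**3. How the last on-treatment value could be <50 c/mL.** Protocol 7.1.4 defines confirmed failure as two consecutive values ≥200 c/mL, so it usually is not. Two routes remain.
- Re-suppression on treatment: Protocol 7.1.5.3 lets a participant with confirmed failure stay on study drug, at the investigator's discretion, until resistance results arrive. A later value can be <50 c/mL before withdrawal.
- All viraemic values fall outside the on-treatment period, for example more than 67 days after the last injection following missed dosing.

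**4. Size.** Protocol Table 6 uses the normal approximation: upper limit = p + 1.96 × √(p(1−p)/n).
- n=100, p=3%: 0.03 + 1.96 × √(0.03 × 0.97/100) = 6.34%, matching the stated 6.3%.
- n=100, p=4%: 0.04 + 1.96 × √(0.04 × 0.96/100) = 7.84%, matching the stated 7.8%.

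One reclassified participant adds 100/n points: 1.1 at n=90, 1.0 at n=100, 0.9 at n=110. The planned total of about 100 covers both regimens, and the size of each treatment group is not given. At an assumed n=50, one participant moves 1/50 = 2% (upper limit 5.9%) to 2/50 = 4% (9.4%). The number affected is not stated; zero is plausible.

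**5. The other proportion.** Both classifications lie outside the <50 c/mL category, and the denominator is all of ITT-E, so the <50 c/mL proportion is unchanged.

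**The case against.** The strongest case is that lack of efficacy in this trial is close to viraemic by definition. Confirmed failure rests on two central-laboratory values ≥200 c/mL, and viral load is scheduled at every treatment visit. The two rules then agree for nearly everyone. This stands, and it limits the point to a rare case.

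Steps 1 to 4 also run first, and a participant with a non-permitted change in therapy before the window is already ≥50 c/mL. This too stands. It does not remove the case unless starting follow-up HAART counts as such a change. On that reading, adverse-event withdrawals who start HAART before the window would also become ≥50 c/mL, against the appendix's own adverse-event example.

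It can also be said that the table is coherent and the examples are pasted text. SAP 7.1.4, 7.2.4 and 12.6.3 all link a non-safety withdrawal to viral load at discontinuation, and one example uses Days 294 to 377, which is not this trial's window. But 12.6.3 is hedged as the typical case, and none of the three sections declares an exception to the FDA rule. The SAP presents the examples as its reference for the algorithm by which the endpoint is defined.

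Finally, there is no hypothesis test. Participants with confirmed failure would still appear in the cumulative virologic failure tables, and withdrawals in the disposition displays and listings. That limits the harm but does not correct the primary row.

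**Conclusion.** The conflict in the text is certain; its numerical effect is probably small and may be nil. Step 5.2.2.2 and the FDA rule in the same appendix give different primary-endpoint classifications for a pre-window lack-of-efficacy withdrawal with no window value, no earlier classification by steps 1 to 4, and a last on-treatment value <50 c/mL or none. Each such participant lowers the ≥50 c/mL proportion by 100/n points. This conclusion rests on the FDA rule as the SAP reproduces it; the guidance itself was not consulted.

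A reader might infer more than the documents support.
- That confirmed failures escape the endpoint because their viraemic values come after long-term follow-up therapy starts. Protocol 7.1.5 says the failure definition does not apply in long-term follow-up, and Protocol 4.2.3 starts HAART once failure is confirmed, so the qualifying values precede it.
- That the DTG + RPV arm, or participants with no on-treatment value, are an equal source. Both are marginal: Protocol 7.1.5.2 asks for at least two weeks of full dosing when the confirmatory sample is drawn, and viral load is scheduled at each visit.
- That virologic failures are dropped in general. Those with a last on-treatment value ≥50 c/mL are counted under both rules.

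**What to change.** In step 5.2.2.2, test lack of efficacy first. Withdrawal for lack of efficacy before the window with no window value becomes HIV-1 RNA ≥50 c/mL, reason discontinued for lack of efficacy, whatever the last on-treatment value, including none. Apply the <50 versus ≥50 c/mL split only to the other non-safety reasons. State how a lack-of-efficacy withdrawal during the window with no window value is handled, since the FDA example covers only withdrawal before it. Add the exception to SAP 12.6.3, 7.1.4 and 7.2.4 so that the summary wording agrees.

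If the current row is intended, list it in SAP 2.1 as a departure from the FDA algorithm and give the reason.

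The cost is one table row, one program condition and a clause in three sections. The primary rate may come out slightly less favourable.

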#### **Examples from FDA guidance**

#### Data in Window

Virologic outcome should be determined by the last available measurement while the patient is on treatment and continued on trial within the time window:

• HIV-RNA = 580 copies/mL at Day 336, HIV-RNA below 50 copies/mL on Day 350. This should be categorized as HIV-RNA below 50 copies/mL.

#### No Data in Window

Discontinued study due to Adverse Event or Death:

- Any patient who discontinues because of an AE or death before the window should be classified as *Discontinued due to AE or Death* (as appropriate), regardless of the HIV-RNA result, even if the HIV-RNA is below 50 copies/mL at the time of discontinuation.
- However, if a patient has an HIV-RNA value in the time window and also discontinues in the time window, the viral load data should be used to classify the patient's response.
   This is the Virology First hierarchy:
  - a. HIV-RNA below 50 copies/mL at Day 336 and discontinues because of AE or even dies on Day 360 — this person is categorized as having HIV-RNA below 50 copies/mL.
  - b. HIV-RNA is 552 copies/mL on Day 336 and the patient discontinues on Day 360, the patient is categorized as having HIV-RNA greater than or equal to 50

copies/mL.

#### Discontinued for Other Reasons:

- Only patients who have achieved virologic suppression can be counted as *Discontinued* for Other Reasons.
- If a patient discontinues the study before the time window because of *lack of efficacy* then the patient should be included in the HIV-RNA greater than or equal to 50 row and not in the Discontinued for Other Reasons row.
- If a patient discontinues because of subject withdrew consent and his or her HIV-1 RNA
  result at the time of discontinuation was equal to or above 50 copies/mL, then he or she
  should be categorized as HIV-RNA greater than or equal to 50 and NOT as
  Discontinued for Other Reasons.
- If a patient discontinued because of *Lost to Follow-Up* and the last HIV-RNA result was 49 copies/mL, then the patient can be categorized as Discontinued for Other Reasons.
- If patients changed background treatment *not permitted by protocol* they should be captured in the HIV-RNA greater than or equal to 50 copies/mL row.

#### On study but missing data in window:

- If there are no data during Days 294 to 377, but there is an HIV-RNA below 50 copies/mL on Day 380, this patient should be considered *On Study but Missing Data in Window*.
- If there are no data during Days 294 to 377, but there is an HIV-RNA equal to or above 50 copies/mL on Day 280, this patient also should be classified as *On Study but Missing Data in Window.*

# 12.10. Appendix 10: Identification of Adverse Events of Special Interest

The adverse events of special interest are identified based on MedDRA coded values and/or AE data available in the study database. The system organ classes (SOCs), preferred terms (PTs) or codes, Standardised MedDRA Queries (SMQs), High Level Group Terms (HLGTs), and High Level Terms (HLTs) below are from MedDRA 22.0. In case there is a change to the version of MedDRA at time of reporting, the coded values based on the MedDRA version at the time of reporting will be used. The additional events may also be added based on the blinded review of AE data collected on study prior to the database freeze.

#### 1. Hepatic Safety Profile

CMO, 'Hanatia Digardara', CMO Cada, 20000005

Medical concept of hepatic failure and hepatitis. Sub- SMQs (1) 'Hepatic failure, fibrosis and cirrhosis and other liver damage-related conditions' and (2) 'Hepatitis, non-infectious', both of parent SMQ 'Hepatic Disorders'; only narrow terms selected from sub-SMQs. Some preferred terms e.g. PT 'hepatitis fulminant' are duplicated.

SMQ: 'Hepatic Disorders'; SMQ Code: 20000005 Sub-SMQ: 'Hepatic failure, fibrosis and cirrhosis and other liver damage-related conditions' Category: A Scope: Narrow		
Preferred Term	PT Code	
Acquired hepatocerebral degeneration	10080860	
Acute hepatic failure	10000804	
Acute on chronic liver failure	10077305	
Acute yellow liver atrophy	10070815	
Ascites	10003445	
Asterixis	10003547	
Bacterascites	10068547	
Biliary cirrhosis	10004659	
Biliary fibrosis	10004664	
Cardiohepatic syndrome	10082480	
Cholestatic liver injury	10067969	
Chronic hepatic failure	10057573	
Coma hepatic	10010075	
Cryptogenic cirrhosis	10063075	

Diabetic hepatopathy	10071265
Drug-induced liver injury	10072268
Duodenal varices	10051010
Gallbladder varices	10072319
Gastric variceal injection	10076237
Gastric variceal ligation	10076238
Gastric varices	10051012
Gastric varices haemorrhage	10057572
Hepatectomy	10061997
Hepatic atrophy	10019637
Hepatic calcification	10065274
Hepatic cirrhosis	10019641
Hepatic encephalopathy	10019660
Hepatic encephalopathy prophylaxis	10066599
Hepatic failure	10019663
Hepatic fibrosis	10019668
Hepatic hydrothorax	10067365
Hepatic infiltration eosinophilic	10064668
Hepatic lesion	10061998
Hepatic necrosis	10019692
Hepatic steato-fibrosis	10077215
Hepatic steatosis	10019708
Hepatitis fulminant	10019772
Hepatobiliary disease	10062000
Hepatocellular foamy cell syndrome	10053244
Hepatocellular injury	10019837
Hepatopulmonary syndrome	10052274
Hepatorenal failure	10019845
Hepatorenal syndrome	10019846

Intestinal varices haemorrhage	Hepatotoxicity	10019851
Liver dialysis 10076640 Liver disorder 10024670 Liver injury 10067125 Liver operation 100224714 Lupoid hepatic cirrhosis 10025125 Minimal hepatic encephalopathy 10066758 Minimal hepatic encephalopathy 10066758 Nodular regenerative hyperplasia 10051081 Nonalcoholic fatty liver disease 10082245 Non-alcoholic steatohepatitis 10053215 Non-cirrhotic portal hypertension 10077255 Oedema due to hepatic disease 10049631 Oesophageal varices haemorrhage 10030210 Peripancreatic varices 1007426 Portal hypertension 1007426 Portal hypertensive colopathy 10068923 Portal hypertensive enteropathy 10068923 Portal vein cavernous transformation 10073205 Portal vein cavernous transformation 10073205 Portopulmonary hypertension 10080267 Portopulmonary hypertension 10073205 Portopulmonary hypertension 10073205 Portopulmonary hypertension 10073205 Portopulmonary hypertension 10073205 Portopulmonary hypertension 10076281 Primary biliary cholangitis 10080425 Regenerative siderotic hepatic nodule 10080675	Intestinal varices	10071502
Liver disorder         10024670           Liver injury         10067125           Liver operation         10062040           Liver transplant         10024714           Lupoid hepatic cirrhosis         10025125           Minimal hepatic encephalopathy         10076204           Mixed liver injury         10066758           Nodular regenerative hyperplasia         10051081           Nonalcoholic fatty liver disease         10082245           Non-alcoholic steatohepatitis         10053215           Non-cirrhotic portal hypertension         10077255           Oedema due to hepatic disease         10049631           Oesophageal varices haemorrhage         10030210           Peripancreatic varices         10073215           Portal hypertension         1007426           Portal hypertensive colopathy         1007426           Portal hypertensive enteropathy         10068923           Portal vein cavernous transformation         10073975           Portal vein dilatation         10073205           Portopulmonary hypertension         10067281           Primary biliary cholangitis         10080678           Regenerative siderotic hepatic nodule         10080678	Intestinal varices haemorrhage	10078058
Liver injury         10067128           Liver operation         10062040           Liver transplant         10024714           Lupoid hepatic cirrhosis         10025128           Minimal hepatic encephalopathy         10076204           Mixed liver injury         10066758           Nodular regenerative hyperplasia         10051081           Nonalcoholic fatty liver disease         10082249           Non-alcoholic steatohepatitis         10073218           Non-cirrhotic portal hypertension         10077259           Oedema due to hepatic disease         10049631           Oesophageal varices haemorrhage         10030210           Peripancreatic varices         10073218           Portal hypertension         10074726           Portal hypertensive colopathy         10074926           Portal hypertensive enteropathy         10068923           Portal vein cavernous transformation         10073978           Portal vein dilatation         10073208           Portopulmonary hypertension         10067281           Primary biliary cholangitis         10080428           Regenerative siderotic hepatic nodule         10080678	Liver dialysis	10076640
Liver operation       10062040         Liver transplant       10024714         Lupoid hepatic cirrhosis       10025129         Minimal hepatic encephalopathy       10076204         Mixed liver injury       10066756         Nodular regenerative hyperplasia       10051081         Nonalcoholic fatty liver disease       10082249         Non-alcoholic steatohepatitis       10053219         Non-cirrhotic portal hypertension       10077259         Oedema due to hepatic disease       10049631         Oesophageal varices haemorrhage       10030210         Peripancreatic varices       10073215         Portal fibrosis       10074726         Portal hypertension       10036200         Portal hypertensive colopathy       1007890         Portal hypertensive enteropathy       10068923         Portal vein cavernous transformation       10073973         Portal vein dilatation       10073208         Portopulmonary hypertension       10067281         Primary biliary cholangitis       10080678         Regenerative siderotic hepatic nodule       10080678	Liver disorder	10024670
Liver transplant       10024714         Lupoid hepatic cirrhosis       10025128         Minimal hepatic encephalopathy       10076204         Mixed liver injury       10066758         Nodular regenerative hyperplasia       10051081         Nonalcoholic fatty liver disease       10082248         Non-alcoholic steatohepatitis       10053218         Non-cirrhotic portal hypertension       10077258         Oedema due to hepatic disease       10049631         Oesophageal varices haemorrhage       10030210         Peripancreatic varices       10073215         Portal fibrosis       10074726         Portal hypertension       10036200         Portal hypertensive colopathy       10079446         Portal hypertensive enteropathy       10050897         Portal vein cavernous transformation       10073205         Portal vein dilatation       10073205         Portopulmonary hypertension       10067281         Primary biliary cholangitis       10080425         Regenerative siderotic hepatic nodule       10080679	Liver injury	10067125
Lupoid hepatic cirrhosis       10025129         Minimal hepatic encephalopathy       10076204         Mixed liver injury       10066758         Nodular regenerative hyperplasia       10051081         Nonalcoholic fatty liver disease       10082249         Non-alcoholic steatohepatitis       10053219         Non-cirrhotic portal hypertension       10077259         Oedema due to hepatic disease       10049631         Oesophageal varices haemorrhage       10030210         Peripancreatic varices       10073218         Portal fibrosis       10074726         Portal hypertension       10036200         Portal hypertensive colopathy       10079446         Portal hypertensive enteropathy       10058923         Portal vein cavernous transformation       10073208         Portal vein dilatation       10073208         Portal vein dilatation       10067281         Primary biliary cholangitis       10080428         Regenerative siderotic hepatic nodule       10080678	Liver operation	10062040
Minimal hepatic encephalopathy       10076204         Mixed liver injury       10066758         Nodular regenerative hyperplasia       10051081         Nonalcoholic fatty liver disease       10082249         Non-alcoholic steatohepatitis       10053219         Non-cirrhotic portal hypertension       10077259         Oedema due to hepatic disease       10049631         Oesophageal varices haemorrhage       10030210         Peripancreatic varices       10073215         Portal fibrosis       10074726         Portal hypertension       10036200         Portal hypertensive colopathy       10079446         Portal hypertensive enteropathy       10068923         Portal vein cavernous transformation       10073205         Portal vein dilatation       10073205         Portal vein dilatation       10073205         Portopulmonary hypertension       10067281         Primary biliary cholangitis       10080425         Regenerative siderotic hepatic nodule       10080675	Liver transplant	10024714
Mixed liver injury       10066758         Nodular regenerative hyperplasia       10051081         Nonalcoholic fatty liver disease       10082249         Non-alcoholic steatohepatitis       10053219         Non-cirrhotic portal hypertension       10077259         Oedema due to hepatic disease       10049631         Oesophageal varices haemorrhage       10030210         Peripancreatic varices       10073218         Portal fibrosis       10074726         Portal hypertension       10036200         Portal hypertensive colopathy       10079446         Portal hypertensive enteropathy       10068923         Portal vein cavernous transformation       10073979         Portal vein dilatation       10073209         Portal vein dilatation       10073209         Portopulmonary hypertension       10067281         Primary biliary cholangitis       10080429         Regenerative siderotic hepatic nodule       10080679	Lupoid hepatic cirrhosis	10025129
Nodular regenerative hyperplasia         10051081           Nonalcoholic fatty liver disease         10082249           Non-alcoholic steatohepatitis         10053219           Non-cirrhotic portal hypertension         10077259           Oedema due to hepatic disease         10049631           Oesophageal varices haemorrhage         10030210           Peripancreatic varices         10073215           Portal fibrosis         10074726           Portal hypertension         10036200           Portal hypertensive colopathy         10079446           Portal hypertensive enteropathy         10050897           Portal vein cavernous transformation         10073979           Portal vein dilatation         10073209           Portopulmonary hypertension         10067281           Primary biliary cholangitis         10080679           Regenerative siderotic hepatic nodule         10080679	Minimal hepatic encephalopathy	10076204
Nonalcoholic fatty liver disease  Non-alcoholic steatohepatitis  Non-cirrhotic portal hypertension  Oedema due to hepatic disease  10049631  Oesophageal varices haemorrhage  Peripancreatic varices  10073215  Portal fibrosis  Portal hypertension  10079446  Portal hypertensive colopathy  Portal hypertensive enteropathy  Portal hypertensive gastropathy  Portal vein cavernous transformation  Portopulmonary hypertension  10073205  Portopulmonary hypertension  10080675  Regenerative siderotic hepatic nodule	Mixed liver injury	10066758
Non-alcoholic steatohepatitis  Non-cirrhotic portal hypertension  Oedema due to hepatic disease  Oesophageal varices haemorrhage  Peripancreatic varices  10073215  Portal fibrosis  Portal hypertension  Portal hypertensive colopathy  Portal hypertensive enteropathy  Portal hypertensive gastropathy  Portal vein cavernous transformation  Portal vein dilatation  Portopulmonary hypertension  Primary biliary cholangitis  Regenerative siderotic hepatic nodule  1007325  1007925  10073215	Nodular regenerative hyperplasia	10051081
Non-cirrhotic portal hypertension 10077258  Oedema due to hepatic disease 10049631  Oesophageal varices haemorrhage 10030210  Peripancreatic varices 10073215  Portal fibrosis 10074726  Portal hypertension 10036200  Portal hypertensive colopathy 10068923  Portal hypertensive enteropathy 10050897  Portal vein cavernous transformation 10073208  Portal vein dilatation 10073208  Portopulmonary hypertension 10067281  Primary biliary cholangitis 10080678	Nonalcoholic fatty liver disease	10082249
Oedema due to hepatic disease 10049631 Oesophageal varices haemorrhage 10030210 Peripancreatic varices 10073215 Portal fibrosis 10074726 Portal hypertension 10036200 Portal hypertensive colopathy 10079446 Portal hypertensive enteropathy 10068923 Portal hypertensive gastropathy 10050897 Portal vein cavernous transformation 10073203 Portopulmonary hypertension 10067281 Primary biliary cholangitis 10080675	Non-alcoholic steatohepatitis	10053219
Oesophageal varices haemorrhage10030210Peripancreatic varices10073215Portal fibrosis10074726Portal hypertension10036200Portal hypertensive colopathy10079446Portal hypertensive enteropathy10068923Portal hypertensive gastropathy10050897Portal vein cavernous transformation10073209Portal vein dilatation10073209Portopulmonary hypertension10067281Primary biliary cholangitis10080429Regenerative siderotic hepatic nodule10080679	Non-cirrhotic portal hypertension	10077259
Peripancreatic varices  Portal fibrosis  Portal hypertension  Portal hypertensive colopathy  Portal hypertensive enteropathy  Portal hypertensive gastropathy  Portal vein cavernous transformation  Portal vein dilatation  Portopulmonary hypertension  Primary biliary cholangitis  Regenerative siderotic hepatic nodule  10073215  10073215  10074726  10079446  10079446  10068923  10068923  10073205  10073205  10067281	Oedema due to hepatic disease	10049631
Portal fibrosis 10074726  Portal hypertension 10036200  Portal hypertensive colopathy 10079446  Portal hypertensive enteropathy 10068923  Portal hypertensive gastropathy 10050897  Portal vein cavernous transformation 10073209  Portopulmonary hypertension 10067281  Primary biliary cholangitis 10080679  Regenerative siderotic hepatic nodule 10080679	Oesophageal varices haemorrhage	10030210
Portal hypertension 10036200 Portal hypertensive colopathy 10079446 Portal hypertensive enteropathy 10068923 Portal hypertensive gastropathy 10050897 Portal vein cavernous transformation 10073979 Portal vein dilatation 10073209 Portopulmonary hypertension 10067281 Primary biliary cholangitis 10080429 Regenerative siderotic hepatic nodule 10080679	Peripancreatic varices	10073215
Portal hypertensive colopathy  Portal hypertensive enteropathy  Portal hypertensive gastropathy  Portal vein cavernous transformation  Portal vein dilatation  Portopulmonary hypertension  Primary biliary cholangitis  Regenerative siderotic hepatic nodule  10079446  10068923  10050897  10073299  10073299  10067281	Portal fibrosis	10074726
Portal hypertensive enteropathy  Portal hypertensive gastropathy  Portal vein cavernous transformation  Portal vein dilatation  Portopulmonary hypertension  Primary biliary cholangitis  Regenerative siderotic hepatic nodule  10068923  10050897  10073979  10073209  10067281	Portal hypertension	10036200
Portal hypertensive gastropathy  Portal vein cavernous transformation  Portal vein dilatation  Portopulmonary hypertension  Primary biliary cholangitis  Regenerative siderotic hepatic nodule  10050897  10073209  10073209  10067281	Portal hypertensive colopathy	10079446
Portal vein cavernous transformation 10073979  Portal vein dilatation 10073209  Portopulmonary hypertension 10067281  Primary biliary cholangitis 10080429  Regenerative siderotic hepatic nodule 10080679	Portal hypertensive enteropathy	10068923
Portal vein dilatation 10073209 Portopulmonary hypertension 10067281 Primary biliary cholangitis 10080429 Regenerative siderotic hepatic nodule 10080679	Portal hypertensive gastropathy	10050897
Portopulmonary hypertension 10067281  Primary biliary cholangitis 10080429  Regenerative siderotic hepatic nodule 10080679	Portal vein cavernous transformation	10073979
Primary biliary cholangitis 10080429  Regenerative siderotic hepatic nodule 10080679	Portal vein dilatation	10073209
Regenerative siderotic hepatic nodule 10080679	Portopulmonary hypertension	10067281
	Primary biliary cholangitis	10080429
Renal and liver transplant 10052279	Regenerative siderotic hepatic nodule	10080679
•	Renal and liver transplant	10052279

Reye's syndrome	10039012
Povnold's syndromo	
Reynold's syndrome	10070953
Splenic varices	10067823
Splenic varices haemorrhage	10068662
Steatohepatitis	10076331
Subacute hepatic failure	10056956
Varices oesophageal	10056091
Varicose veins of abdominal wall	10072284
White nipple sign	10078438

Category: A Scope: Narrow

Preferred Term	PT Code
Acute graft versus host disease in liver	10066263
Allergic hepatitis	10071198
Alloimmune hepatitis	10080576
Autoimmune hepatitis	10003827
Chronic graft versus host disease in liver	10072160
Chronic hepatitis	10008909
Graft versus host disease in liver	10064676
Hepatitis	10019717
Hepatitis acute	10019727
Hepatitis cholestatic	10019754
Hepatitis chronic active	10019755
Hepatitis chronic persistent	10019759
Hepatitis fulminant	10019772
Hepatitis toxic	10019795
Immune-mediated hepatitis	10078962

Ischaemic hepatitis	10023025
Lupus hepatitis	10067737
Non-alcoholic steatohepatitis	10053219
Radiation hepatitis	10051015
Steatohepatitis	10076331

